4.1.4.3 BI 836858 dose reduction and dose escalation criteria

Administration of the trial drugs (i.e. both, decitabine and BI 836858 for patients receiving the combination treatment) has to be stopped temporarily in case of a DLT (see [Section 5.3.1](#)). Patients may continue therapy only after recovery from the DLT to a CTCAE level which allows further therapy based on Investigator assessment and only with a reduced dose of BI 836858. No dose levels for the new dose of BI 836858 have been pre-defined; any new dose outside of the currently tested dose level/cohort must be finally agreed on between the Sponsor and the Investigator. The reduced dose will be valid for all following treatment cycles in the individual patient. A reduction of the dose will be allowed only once for an individual patient during the whole trial. In case a patient experiences a second episode of DLT with the reduced BI 836858 dose, the treatment with BI 836858 has to be permanently discontinued. Likewise, treatment with BI 836858 has to be discontinued in case the DLT is not reversible. In Phase I such patients will need to be withdrawn from study treatment, perform EOT and EoR visits and followed-up as per protocol. Patients in Arm 1 of Phase II however may continue on decitabine monotherapy at the discretion of the investigator.

Intra-patient dose escalation

Intra-patient dose escalation may be considered in agreement between the Investigator and Sponsor for selected patients. It is restricted to patients who have received at least 4 administrations of BI 836858 and tolerated the treatment well up to the time of dose escalation. Intra-patient dose escalation can only be performed at a time when the next higher dose cohort has been reviewed and considered safe by the SMC. The dose escalation step is limited to the dose which has been administered to the next higher cohort. In addition, after the first dose at the higher dose level, patients have to be monitored for at least 24 h after the end of the infusion, including safety laboratory 24 h after the first administration of the escalated dose of BI 836858.

Patients eligible for a subsequent treatment cycle will not start treatment before 28 days after the start of the previous cycle. If the criteria above ([Section 4.1.4.2](#)) are not met on Day 29, the subsequent cycle must be delayed. The period of delay is limited to a maximum of 8 weeks. Re-treatment should be initiated as soon as the criteria are met, unless other criteria for discontinuation or withdrawal apply, according to [Sections 3.3.4](#) and [4.1.4.2](#). Any delay of more than three weeks between the end of the previous and the start of the next treatment cycle should be communicated to the clinical monitor of BI prior to re-treatment.

4.1.5 Blinding and procedures for unblinding

4.1.5.1 Blinding

This is an open-label study (see [Section 3.2](#) for justification). Blinding is not applicable on individual patient level. However, to reduce bias, the BI study team will be blinded for the aggregated Phase II part data at the treatment level until the trial database lock.

4.1.5.2 Unblinding and breaking the code

Not applicable.

4.1.6 Packaging, labelling, and re-supply of BI 836858

BI 836858 will be supplied in 10 mL vials containing 100 mg BI 836858. For details of packaging and the description of the label, refer to the ISF. Medication will be delivered to the Investigator's pharmacy where the total dose per patient will be prepared upon request from the Investigator.

For preparation of BI 836858 infusion solution, the content of the vial of BI 836858 will be diluted in 0.9% sodium chloride. The content of several vials may be needed for administration of the requested dose. For further details, please refer to the instructions included in the ISF. The full volume of the diluted compound will be 250 ml.

Re-supply of BI 836858 will be managed by IRT.

4.1.7 Storage conditions

Trial drug supplies will be kept in their original packaging and in a secure limited access storage area according to the recommended storage conditions on the medication label. A temperature log must be maintained for documentation.

If the storage conditions are found to be outside the specified range, the local clinical monitor (as provided in the list of contacts in the ISF) must be contacted immediately and the corresponding procedures described in the ISF need to be followed.

4.1.8 Drug accountability

The Investigator and/or Pharmacist will receive the trial drug(s) delivered by the Sponsor or a CRO appointed by the Sponsor when the following requirements are fulfilled:

- Approval of the trial protocol by the IRB / ethics committee,
- Availability of a signed and dated clinical trial contract between the Sponsor and the head of the investigational site,
- Approval/notification of the regulatory authority, e.g. competent authority,
- Availability of the *curriculum vitae* of the principal Investigator,
- Availability of a signed and dated clinical trial protocol
- Availability of the proof of a medical license for the principal Investigator
- Availability of Form 1572 or equivalent

The Investigator and/or Pharmacist must maintain records of the product's delivery to the trial site, the inventory at the site, the use by each patient, and the return to the Sponsor or alternative disposal of unused products.

These records will include dates, quantities, batch / serial numbers, expiry ('use- by') dates, and the unique code numbers assigned to the investigational product and trial patients. The Investigator / Pharmacist will maintain records that document adequately that the patients were provided the doses specified by the CTP and reconcile all investigational products received from the Sponsor. At the time of return to the Sponsor and/or appointed CRO and/or

prior to local destruction of any unused trial medication, the Investigator / Pharmacist must verify that all unused or partially used drug supplies have been fully accounted for on appropriate drug accountability/ drug inventory logs and that no remaining supplies are in the Investigator's possession.

The only exception to the above will be commercial decitabine that will be sourced locally by participating trial sites/pharmacies from local suppliers (if allowed by local regulations). In that case drug accountability (including details as described above) will be done on patient and site level only, without detailed records of the product's delivery to the trial site.

4.2 CONCOMITANT THERAPY, RESTRICTIONS, AND RESCUE TREATMENT

4.2.1 Rescue medication, emergency procedures, and additional treatment(s)

Rescue medication to reverse the action of BI 836858 is not available. Potential side effects of BI 836858 have to be treated symptomatically. Patients should receive supportive care according to the local guidelines regarding treatment of infusion-related reactions, blood product support, antibiotics, antivirals, analgesics, skin and mouth care, etc. The use of growth factors such as granulocyte colony stimulating factor will be allowed, but growth factors should be avoided during the first four administrations of BI 836858 for better assessment of safety and response parameters.

Anti-infective prophylaxis

Based on the known myelosuppressive effect of decitabine, patients should receive anti-infective prophylaxis as follows:

- Antibiotic prophylaxis: it is mandatory that patients receive prophylaxis with antibiotics when absolute neutrophil count (ANC) counts are $< 500/\mu\text{L}$. This prophylaxis should be continued at least until the ANC counts have reached $\geq 500 \text{ cells}/\mu\text{L}$ and can be prolonged if clinically appropriate. Antibiotics used for infection prophylaxis should be selected based on institutional and published guidelines ([R15-3877](#), [R15-4167](#)) as well as on patient-specific medical considerations.
- Antimycotic prophylaxis: surveillance for mycotic infections should be maintained during therapy, mainly in patients with persistent and long-lasting neutropenia. Antimycotic prophylaxis is recommended and should be implemented at discretion of Investigator when deemed medically necessary.

Prevention and treatment of Tumor Lysis Syndrome (TLS)

Risk for TLS should be assessed as per published guidelines prior to starting treatment with BI836858 ([R18-1901](#)). All patients should receive adequate hydration prior to start of each administration of BI 836858 in Cycle 1. Prophylactic administration of anti-hyperuricaemic agents (e.g. allopurinol, rasburicase) should be considered according to individual patient risk. Laboratory monitoring for TLS is mandatory as outlined in [Table 1](#) and [Section 5.3.6.1](#). In patients developing laboratory or clinical signs of a tumor lysis syndrome (e.g. hyperkalemia, hyperphosphatemia, hyperuricemia and hyperuricosuria, hypocalcemia, and acute renal failure), accepted treatments standards as per published recommendations must be applied ([R18-1901](#), [R10-4517](#)).

All concomitant non-anti-leukemia therapies to provide adequate care may be given as clinically necessary. All concomitant treatments will be recorded in the eCRF except for vitamins and nutrient supplements. Trade name, indication and dates of administration of concomitant therapies will be documented. For parenteral nutrition during the trial, the components need not be specified in detail. It should be indicated as 'parenteral nutrition'. If a patient needs anesthesia, it will be sufficient to indicate 'anesthesia' without specifying the details.

4.2.2 Restrictions

4.2.2.1 Restrictions regarding concomitant treatment

In patients with relapsed or refractory AML, prior anti-leukemia therapy must have been discontinued at least two weeks before first treatment with decitabine and the patient must have recovered from all clinically relevant reversible toxicities as determined by the Investigator. A time interval of at least two weeks (four weeks for biologicals) must have elapsed from the last administration of any other investigational treatment for AML to the first administration of BI 836858.

For WBC control (e.g. to keep WBC < 10,000/ μ L), treatment with hydroxyurea will be allowed during Cycle 1 only.

No other concomitant anti-neoplastic therapy is allowed during the treatment phase of this trial.

Short term glucocorticoid medications may be used as clinically indicated to treat infusion-related reactions at any dose. All other indications for steroids have to be discussed and agreed upon between Investigator and Sponsor.

Intrathecal treatment to control symptoms associated with central nervous system involvement is allowed but must be discussed and agreed upon between Investigator and Sponsor. All concomitant therapy will be recorded in the eCRF.

No formal clinical drug-drug interaction studies with BI 836858 have been conducted for decitabine. For restrictions regarding concomitant treatment with decitabine, refer to manufacturer's SPC ([R15-4802](#)).

4.2.2.2 Restrictions on diet and life style

No restrictions apply with regard to diet or life style. However, patients are required to be hospitalized for approximately 48 h after start of the first administration of BI 836858 to allow close monitoring for infusion-related reactions or other AEs. Subsequent infusions of BI 836858 may be administered in the out-patient setting depending on the Investigator's decision.

4.3 TREATMENT COMPLIANCE

BI 836858 will be administered as a single i.v. infusion under supervision of the Investigator or dedicated clinic personnel. Compliance may also be verified by PK assessment. Any discrepancies will be explained in the eCRF by the Investigators or their designee. Decitabine will be administered as an i.v. infusion under the supervision of the Investigator or designated personnel at the investigative site according to the manufacturer's product information (available in the ISF). Administration of decitabine will also be documented in the eCRF.

5. VARIABLES AND THEIR ASSESSMENT

5.1 TRIAL ENDPOINTS

5.1.1 Primary Endpoints

In the Phase I part of this trial, the primary endpoints to assess safety are the MTD of BI 836858 in combination with decitabine and the number of patients with DLTs during the first treatment cycle. For details on determination of MTD, please refer to [Section 5.3.2](#) and [7.1](#).

In the Phase II part of the trial, the primary objective is to assess the preliminary efficacy of BI 836858 in combination with decitabine in comparison to standard therapy with decitabine alone. The primary endpoint in Phase II is objective response (CR+CRi) defined as best overall response of CR or CRi, analyzed by the number of patients with CR or CRi. None of the endpoints listed below are assessing known safety issues.

Phase I:

- MTD of BI 836858 in combination with decitabine
- Number of patients with DLTs during the first treatment cycle (see [Section 5.3.2](#))
- Time frame: From start of treatment until end of cycle 1 (end of REP; approximately up to 12 months).

Phase II:

- Number of patients with objective response combining
 - Complete remission (CR)
 - CR with incomplete blood count recovery (CRi)
- Time frame: From randomization until the earliest of progression, death or end of trial (approximately up to 30 months).

5.1.2 Secondary Endpoints

The secondary endpoint of the Phase I part of this trial is objective response (CR/CRi) as defined in [Section 5.2.1](#). Secondary endpoints of the Phase II part of this trial are event-free survival (EFS), relapse-free survival (RFS), remission duration and time to remission.

None of the endpoints listed below are assessing known safety issues.

Phase I:

- Number of patients with objective response combining
 - Complete remission (CR)
 - CR with incomplete blood count recovery (CRi)
- Time frame: From start of treatment until the earliest of progression, death or end of trial (approximately up to 30 months).

Phase II:

- Event-free survival (EFS)
- Relapse-free survival (RFS)
- Remission duration
- Time to remission

Event-free survival (EFS):

- EFS is measured from the date of randomization to the date of progression, relapse, or death from any cause, whichever occurs first.
- The date of progression/relapse will be the earliest of the dates of the disease assessment (blood sample, bone marrow sample, or clinical assessment) in which the progression/relapse was observed. For patients who did not progress, relapse, or die, EFS will be censored at the date of last disease assessment. Patients who stopped active treatment will be followed up as described in [Section 6.2.3](#).
- Time frame: From randomization until the earliest of progression, relapse, death or end of trial (approximately up to 30 months).

Relapse-free survival (RFS):

- RFS is defined only for patients who achieve a best overall response of CR or CRI and is measured from the date of first occurrence of CR or CRI until the date of relapse or death from any cause, whichever occurs first.
- The date of relapse will be the earliest of the dates of the disease assessment (blood sample, bone marrow sample, or clinical assessment) in which the relapse was observed. Patients not known to have relapsed or died at last follow-up are censored on the date they were last examined. Patients who stopped active treatment will be followed up as described in [Section 6.2.3](#).
- Time frame: From first documented response of CR or CRI until the earliest of relapse, death or end of trial (approximately up to 30 months).

Remission duration:

- Remission duration is defined analogously to RFS only for patients with a best overall response of CR or CRI, with the exception of censoring patients who die before recurrence; i.e. remission duration is measured from the date of first occurrence of CR or CRI until the date of relapse.
- The date of relapse will be the earliest of the dates of the disease assessment (blood sample, bone marrow sample, or clinical assessment) in which the relapse was observed. For patients who die or are lost to follow-up without documented relapse, remission duration will be censored, respectively, on the date of death, regardless of cause, or on the date of last disease assessment for the patients who are alive when lost to follow-up.
- Time frame: From first documented response of CR or CRI until the earliest of relapse or end of trial (approximately up to 30 months).

Time to remission:

- Time to remission is defined only for patients who achieve a best overall response of CR or CRI; it is measured from the date of randomization until the date of first achieving CR or CRI.
- Time frame: From randomization until the first documented response of CR or CRI (approximately up to 30 months).

5.2 ASSESSMENT OF EFFICACY

5.2.1 Overall response assessment

Response to treatment will be evaluated based on bone marrow samples (aspirations and biopsies will be collected as described in the [Flow Chart](#)) according to the following criteria (based on diagnosis and management of AML in adults: recommendations from an international expert panel, on behalf of the European Leukemia Net ([R10-2947](#))

- Complete remission (CR)
Bone marrow (BM) blasts < 5%; absence of blasts with Auer rods; absence of extramedullary disease; absolute neutrophil count $> 1.0 \times 10^9/L$ [1,000/ μ L]; platelet count $> 100 \times 10^9/L$ [100,000/ μ L]; independence of red blood cells transfusions (no transfusion for 1 week prior to the assessment). No minimum duration of response is required.
- Complete remission with incomplete neutrophil or platelet recovery (CRi)
All CR criteria except for residual neutropenia ($< 1.0 \times 10^9/L$ [1,000/ μ L]) or thrombocytopenia ($< 100 \times 10^9/L$ [100,000/ μ L]).
- Partial remission (PR)
All haematologic criteria of CR; decrease of bone marrow blast percentage to 5% to 25%; and decrease of pre-treatment bone marrow (baseline) blast percentage by at least 50%. Bone marrow samples with <5% blasts and with presence of Auer rods also represent PR.
- Stable disease (SD)
Patient alive with no CR, CRi, PR or PD.
- Progressive disease (PD)
Progressive disease is defined as at least one of the criteria below:
 - 50% increase in BM blast count over baseline (AML diagnosis);
 - 50% increase in peripheral blast count over baseline that is considered clinically relevant by the Investigator;
 - evidence of new extramedullary disease;

Proprietary confidential information © 2019 Boehringer Ingelheim International GmbH or one or more of its affiliated companies

- clinically progressive disease based on the judgement of the Investigator (any attempt should be made to verify clinically diagnosed PD by a BM assessment).
- Relapse (recurrence)
In patients with previous CR or CRi: Bone marrow leukemic blasts $\geq 5\%$ or reappearance of blasts in the blood not attributable to any other cause (e.g. bone marrow regeneration), or development of extramedullary disease.
- Death in aplasia
Deaths occurring ≥ 7 days following completion of treatment cycle while cytopenic; with an aplastic or hypoplastic bone marrow obtained within 7 days of death, without evidence of persistent leukemia. Completion of treatment cycle is defined as reaching of Day 28 of the cycle.
- Death from indeterminate cause
Deaths occurring before completion of a treatment cycle, or < 7 days following its completion; or deaths occurring ≥ 7 days following completion of treatment course with no blasts in the blood, but no bone marrow examination available. Completion of treatment cycle is defined as reaching Day 28 of the cycle.

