5.2.2 Secondary endpoint(s)

Phase I

- Number of subjects with objective response combining
 - Complete remission (CR)
 - CR with incomplete blood count recovery (CRI)

- Time frame: From start of treatment until the earliest of progression, death or end of trial (approximately up to 30 months).

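### Neutrophil or platelet counts exactly at the CR limits fit neither CR nor CRi, so that assessment falls to stable disease

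*Protocol*

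**What the plan says.** Protocol 5.2.1 (Overall response assessment) sets the response categories:

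- **CR** requires marrow blasts below 5%, no Auer rods, no extramedullary disease, red-cell transfusion independence, neutrophils strictly greater than 1.0 × 10^9/L and platelets strictly greater than 100 × 10^9/L.
- **CRi** is "All CR criteria except for residual neutropenia", given as strictly less than 1.0 × 10^9/L, or thrombocytopenia, given as strictly less than 100 × 10^9/L.
- **PR** starts from "All haematologic criteria of CR; decrease of bone marrow blast percentage to 5% to 25"%. The only route to PR with blasts under 5% needs Auer rods.
- **SD** is the residual class: "Patient alive with no CR, CRi, PR or PD".

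Protocol 5.1.2 makes objective response (CR/CRi), as defined in 5.2.1, the Phase I secondary endpoint. SAP 5.2.2 repeats it as "Number of subjects with objective response combining" CR and CRi, without restating the count limits. SAP 7.5 plans a listing, with aggregated tables only if they seem useful. SAP 6.6 covers missing data and outliers but not values equal to a limit.

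**The concern.** All four inequality signs are strict, so the two definitions leave a gap at the limits themselves. A patient with a cleared marrow, adequate neutrophils and platelets of exactly 100 is stable disease. The same patient with 99 would be CRi and with 101 would be CR. Response then does not follow the order of the counts, which cannot be intended. Elsewhere in 5.2.1 the boundaries do meet: CR needs blasts below 5%, and relapse starts at 5% or more.

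At stake is the classification of single assessments in the Phase I response listing and in any table built from it. With no stated rule, sites or programmers could resolve the same tie differently.

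**Working it through.** The plan gives no figure for this point. Its only figures built on CR+CRi are the Phase II probabilities in Protocol 7.7. Phase II was cancelled (SAP 3 and 4), and those figures do not bear on how an assessment is classified. The check is therefore one of logic, followed by simple proportions.

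**Inputs.** The limits come from Protocol 5.2.1. The patient numbers come from the Protocol synopsis: 16 entered in Dose Escalation and 33 in the Extension, so 16 + 33 = 49.

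**Rules as written.** Let A be the neutrophil count and P the platelet count, both in 10^9/L, with all other CR criteria met.

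- CR: A > 1.0 and P > 100.
- CRi: not CR, and A < 1.0 or P < 100.
- Neither: (A = 1.0 and P ≥ 100) or (A ≥ 1.0 and P = 100).

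**Applied to values around the limits:**

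| | P = 99 | P = 100 | P = 101 |
|---|---|---|---|
| A = 0.9 | CRi | CRi | CRi |
| A = 1.0 | CRi | **SD** | **SD** |
| A = 1.1 | CRi | **SD** | CR |

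Three of the nine combinations meet neither definition.

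**Why they end in SD.** PR fails twice: its blood-count requirement is that of CR, which a tie does not meet, and its blast range starts at 5%. A cleared marrow with no new disease does not meet PD. SD is what remains.

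**Effect of closing the gap.** If CRi is taken at A ≤ 1.0 or P ≤ 100, or CR at A ≥ 1.0 and P ≥ 100, all nine combinations become CR or CRi. The number with CR+CRi is the same either way. Only the split between CR and CRi moves.

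**Size of one reclassified patient.**

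- All Phase I patients: 1/49 = 2.0 percentage points.
- Extension: 1/33 = 3.0 percentage points.

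These are the arithmetic of one patient, not an estimate of how many would be affected.

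**The case against.** The best case for leaving the text alone is that the gap needs an exact tie, the consequence is minor, and a clinician would settle it sensibly. Response is assessed locally (Protocol 6.2.2), and the full name of the CRi category, which refers to incomplete neutrophil or platelet recovery, points a reader towards CRi. The visible SAP text does not show these inequalities being programmed. Phase I response is listed, with no visible test or decision threshold on the rate. All of this stands as a limit on the weight of the point. It does not remove the gap in the written rule.

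Four stronger readings are tempting but not supported:

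- **That any count at its limit rules out both categories.** On the strictest reading, each count must be clearly above or clearly below its limit, and five of the nine combinations would be unclassified. CRi, however, is satisfied by low neutrophils or low platelets. With one count at its limit and the other below, an ordinary reading gives CRi.
- **That a tie loses the responder.** Protocol 5.1.1 defines objective response as best overall response (stated for Phase II), and 5.2.1 requires no minimum duration for CR. Marrow is scheduled at the end of Cycles 1 and 2 and every other cycle thereafter, so a later assessment may qualify. This protection is partial: scheduled marrows can be two cycles apart, and after approval of protocol version 7.0 they are at the investigator's discretion.
- **That CR+CRi is the only Phase I efficacy endpoint.** It is the only visible secondary one. Protocol 7.3 mentions further efficacy endpoints, and parts of both documents are redacted.
- **That ties are likely because neutrophils are reported to one decimal.** The documents do not state the reporting precision. Protocol 5.2.1 also gives the limits per microlitre (1,000 and 100,000), and ties are rarer in finer units.

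**Conclusion.** The point holds as a minor drafting error in an endpoint definition. An assessment with all other CR criteria met, at least one count exactly at its limit and neither below it is stable disease under Protocol 5.2.1 as written, and no visible SAP text corrects this. That assessment is lost to CR+CRi. The patient is lost only if no other assessment qualifies.

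The effect is probably very small. The frequency of ties is not documented, so no expected number of affected patients can be given. The sizes of 2.0 and 3.0 percentage points assume exactly one such patient and denominators of 49 and 33.

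**What to change.** Add to SAP 5.2.2:

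> For the analysis of objective response, when all other CR criteria are met, a neutrophil count of exactly 1.0 × 10^9/L or a platelet count of exactly 100 × 10^9/L is treated as incomplete recovery, and the assessment is classed as CRi.

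If the SAP is no longer open to change, the same sentence can stand as a footnote to the response listing. In either case, check the listing for assessments recorded as SD with marrow blasts below 5% and a count at its limit. With 49 patients this is a short task. The choice of side cannot alter the CR+CRi total.

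Keep the rule to the analysis. CR and CRi status also governs the change from weekly to monthly BI 836858 (Protocol 4.1.3.1, 4.1.3.2 and 4.1.4), and the definition of relapse in 5.2.1 depends on an earlier CR or CRi. A change to the 5.2.1 wording would reach those passages and would need a protocol amendment after recruitment has ended. If the sponsor wishes to change it, the sponsor must reconcile those passages. No position is taken here on the treatment rules.
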